#### 4.1.2. Exclusion Criteria

Subjects who meet any of the following criteria will be disqualified from entering the study:

1. Left ventricular ejection fraction (LVEF) <50%
2. Prior EGFR targeted regimen
3. No HRG expression result
4. No HPV or p16 status
5. Prior anti-HER3 therapy
6. Prior chemotherapy for recurrent/metastatic disease
7. Anti-cancer therapy between biopsy and submission of sample
8. Presence of squamous cell tumors of the nasopharynx
9. History of other malignancies, except adequately treated non-melanoma skin cancer, curatively treated in-situ disease, or other solid tumors curatively treated with no evidence of disease for  $\geq 2$  years
10. Known history of brain metastases or active brain metastases
11. Uncontrolled hypertension (systolic > 160 mm Hg or diastolic > 100 mm Hg)
12. Clinically significant electrocardiograph (ECG) findings
13. Myocardial infarction within 1 year before enrollment, symptomatic congestive heart failure (New York Heart Association >Class II), unstable angina, or unstable cardiac arrhythmia requiring medication
14. Platinum-containing drug therapy with radiotherapy less than 6 months before study drug treatment
15. Therapeutic or palliative radiation therapy or major surgery within 4 weeks before study drug treatment. Radiation treatment to all sites of measureable disease unless progression is documented after radiation
16. Participated in clinical drug trials within 4 weeks before study drug treatment. Current participation in other investigational procedures
17. Uncontrolled infection requiring IV antibiotics, antivirals, or antifungals, known HIV infection, or active hepatitis B or C infection or undergoing medical treatment for infection
18. Uncontrolled type 1 or 2 diabetes mellitus
19. Known hypersensitivity or allergic reaction against any of the components of the trial treatment
20. Pregnant, breastfeeding, or unwilling/unable to use acceptable contraception
21. Residual toxicities  $\geq$  Grade 1 from previous therapies that the Investigator determines would exclude participation

22. Psychological, social, familial, or geographical factors that would interfere with study participation or follow-up
23. Committed to an institution by virtue of an order issued either by judicial or administrative authorities
24. Employee or immediate relative of an employee of the sponsor, CRO, the study center, or their affiliates or partners
25. Receiving yellow fever vaccine or live attenuated vaccines (for subjects receiving carboplatin)
26. Presence of hemorrhagic tumors (for subjects receiving carboplatin)
27. Prophylactic use of phenytoin or fosphenytoin (for subjects receiving cisplatin or carboplatin)

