  25. Receiving yellow fever vaccine or live attenuated vaccines (for subjects receiving carboplatin)
  26. Presence of hemorrhagic tumors (for subjects receiving carboplatin)
  27. Prophylactic use of phenytoin or fosphenytoin (for subjects receiving cisplatin or carboplatin)
- 

Dosage Form, Dose and  
Route of Administration:

Patritumab

Placebo lyophilisate will be diluted in an identical manner in 8 mL water.

The order of IV administration will be:

1. Patritumab or placebo
  - Patritumab/placebo initial loading dose [REDACTED] over 60 minutes ( $\pm$  10 minutes) followed in cycle 2 and beyond with a maintenance dose of [REDACTED] over 60 minutes ( $\pm$  10 minutes) every three weeks
    - Infusion time can be extended to a maximum of 120 minutes for subjects unable to tolerate the 60 minute infusion
2. Cetuximab
  - Cetuximab initial dose at 400 mg/m^2 IV as a 2-hour infusion on Week 1, followed by 250 mg/m^2 over 60 minutes weekly, plus

One hour after the end of the cetuximab administration infuse with either:

3. Cisplatin OR carboplatin selected at the discretion of the Investigator.
    - Cisplatin at 100 mg/m^2 IV infused over 1 hour, every three weeks up to a maximum of 6 cycles
      - Pretreatment hydration with 2 liters of fluid prior to a cisplatin infusion is recommended and should adhere to institutional standards.
-

Adequate hydration and urinary output must be maintained during the following 24 hours. Other pretreatments such as anti-emetic prophylaxis and post-treatments such as hydration are up to the discretion of the Investigator.

OR

- Carboplatin, at AUC 5 IV bolus over 30 to 60 minutes, every 3 weeks for a maximum of 6 cycles. The carboplatin dose will be calculated using the Calvert formula:
  - AUC 5 is the target
  - Carboplatin Dose (mg) = 5 x ([glomerular filtration rate] GFR + 25)
  - Estimated serum creatinine clearance (mL/min) calculated using the modified Cockcroft-Gault equation ([Appendix 17.1](#)) can also be used as an estimate for GFR
  - The carboplatin dose is required to be re-calculated for every dosing based on the current GFR (or creatinine clearance as an estimate of GFR as per the protocol)
  - Pre- and post-treatments are up to the discretion of the investigator

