#### **5.1.7. Guidelines For Dose Modifications**

For those subjects who continue treatment, the Investigator will evaluate which hematological and/or non-hematological toxicities are attributed to which drug(s), and adjust the dose of one or more of the drugs as recommended below.

If a subject experiences an unacceptable toxicity to cisplatin, the Investigator will be able to withhold drug, reduce dose, or switch to carboplatin. If the Investigator chooses to start treatment with carboplatin, then carboplatin will be administered throughout the study. If a subject also experiences an unacceptable toxicity to carboplatin, then carboplatin treatment will be withheld or dose reduced.

Subjects with unacceptable toxic effects of one of the study drugs will receive only the tolerated drugs until disease progression.

- If patritumab/placebo needs to be discontinued, the subject will be withdrawn from the study
- In subjects whose cisplatin or carboplatin therapy is discontinued, reduced, or delayed, the patritumab and cetuximab will be continued and subjects will continue to undergo tumor assessments at 6 week intervals until disease progression or unacceptable toxicity
- In subjects whose cetuximab dose is discontinued, reduced, or delayed, the patritumab will be continued. Cisplatin or carboplatin will be administered for a maximum of 6 cycles
- In subjects whose cetuximab and cisplatin or carboplatin are either discontinued or delayed, patritumab will be continued as monotherapy

In addition to the recommendations provided below, please refer to the respective current prescribing information for detailed recommendations on managing suspected toxicities, for guidance on withholding, dose reductions, and discontinuation. If toxicities occur, it is up to the discretion of the Investigator to dose reduce or withhold one or more medications until recovery or resolution of the AE to Grade 0 or 1.

In individual cases, if a subject discontinues study drugs for an extended time period, the subject may restart study drugs at the discretion of the investigator after discussion with the Sponsor and CRO's medical monitors.

Investigators may contact the Sponsor's medical monitor to discuss any question regarding dose modification or discontinuation of study drugs.

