**Table 5.5: Cisplatin Dose Modifications and Discontinuations\* for Toxicities**

Toxicity	Dose Modification/Discontinuation
Hematological	A repeat course should not be given until circulating blood elements are at an acceptable level (ie, platelets $\geq 100 \times 10^9/L$ , white blood cells $\geq 4 \times 10^9/L$ )
Febrile neutropenia/infection	The first episode of febrile neutropenia or infection will result in reduction by 20% of cisplatin dose. If there is a second episode, despite dose reduction, the subject must receive prophylactic antibiotics during subsequent cycles. If there is a third episode, the subject will be withdrawn from study.
Neutropenia	Grade 2 or 3: cisplatin treatment delay until < Grade 1. Grade 4: cisplatin treatment delay until < Grade 1; dose reduction of all further doses of cisplatin by 20%.
Nephrotoxicity	A repeat course of cisplatin should not be given until the serum creatinine is below 1.5 mg/100 mL, and/or the urea is below 25 mg/100 mL
Thrombocytopenia	Grade 1: cisplatin treatment delay until platelets $\geq 100,000/mm^3$ . $\geq$ Grade 2: cisplatin treatment delay until platelets $>100,000/mm^3$ , dose reduction of all further doses of cisplatin by 20%

Toxicity	Dose Modification/Discontinuation
Organ Toxicity	Grade 2: Delay chemotherapy until $\leq$ Grade 1. $\geq$ Grade 3 or more: Delay chemotherapy until $\leq$ Grade 1; dose reduction of all further doses of cisplatin by 20%. Do not delay or reduce cisplatin dose if there are asymptomatic increases in transaminases, cetuximab-induced skin reactions, and subclinical side effects (e.g. nausea, vomiting, alopecia, altered taste).
Ototoxicity	Criteria for hearing testing
Neuropathy	In case of sensory neuropathy $\geq$ Grade 2, change cisplatin to carboplatin

Note: Please refer to the cisplatin package insert for additional information on potential toxicities and their management. When cisplatin is administered in combination with other agents such as cetuximab, refer to their respective product information. \*If events do not recover within 3 weeks, discontinue cisplatin treatment.

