##### *Hematological toxicity*

Leukopenia, neutropenia, and thrombocytopenia are dose-dependent and dose-limiting. Anemia is frequent and cumulative. Frequent monitoring of peripheral blood counts is recommended during and following therapy. Carboplatin should not be repeated until after leukocytes, platelets, and neutrophils have returned to normal ([Table 5.6](#)).

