#### 6.2.8. Every 6 Weeks

- Frequency of tumor assessments will be every 6 weeks to Week 24 ( $\pm 3$  days); every 12 Weeks ( $\pm 7$  days) thereafter

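### The hemorrhagic-tumor exclusion for carboplatin is applied at study entry but is not repeated where the protocol allows or instructs a later switch from cisplatin to carboplatin

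*Protocol*

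**What the plan says.** Exclusion 26 in Protocol Section 4.1.2 reads "Presence of hemorrhagic tumors (for subjects receiving carboplatin". The same criterion stands in the protocol synopsis and the SAP synopsis. The sentence that opens the list in 4.1.2 is "Subjects who meet any of the following criteria will be disqualified from entering the study".

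The platinum agent is not randomized. The dosing part of the protocol synopsis gives it as "Cisplatin OR carboplatin selected at the discretion of the Investigator".

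Two places deal with moving from cisplatin to carboplatin after treatment has begun:

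- Section 5.1.7, for unacceptable cisplatin toxicity, lets the Investigator "withhold drug, reduce dose, or switch to carboplatin".
- The neuropathy row of Table 5.5 (Section 5.1.7.3), for sensory neuropathy at or above the stated grade, says "Grade 2, change cisplatin to carboplatin".

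Section 5.1.7 also covers what happens to the other drugs when platinum is cut back: "In subjects whose cisplatin or carboplatin therapy is discontinued, reduced, or delayed, the patritumab and cetuximab will be continued".

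**The concern.** The sponsor decided that a subject with a hemorrhagic tumor should not be given carboplatin in this trial. The restriction is written as an entry criterion tied to one of two interchangeable drugs, and the protocol provides a route from the other drug to that one. A subject who enters properly on cisplatin with a hemorrhagic tumor, and then develops cisplatin toxicity, can be moved to carboplatin by following the dose-modification text as written. At entry the protocol would have excluded that subject from carboplatin.

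What is at stake is the safety of the individual subject. The protocol itself says of carboplatin, in Section 5.1.7.4: "Leukopenia, neutropenia, and thrombocytopenia are dose-dependent and dose-limiting". A low platelet count is an obvious worry in a subject whose tumor bleeds. Nothing in the randomization, the PFS endpoint, the event count or the testing procedure depends on this.

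**Working it through.** No figure in the plan bears on this point, so the check is a comparison of texts.

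**Step 1: the route.** (a) The exclusion list acts at entry, and exclusion 26 concerns carboplatin subjects only. (b) The Investigator picks the platinum, so a subject with a hemorrhagic tumor may enter on cisplatin. (c) On cisplatin toxicity, 5.1.7 offers carboplatin as one of three options; for sensory neuropathy of Grade 2 or higher, Table 5.5 names carboplatin as the action. (d) Neither text carries a hemorrhagic-tumor condition.

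**Step 2: is the restriction picked up elsewhere?** I compared exclusion 26 with the other platinum-related entry rules.

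| Entry rule | Platinum concerned | Counterpart during treatment |
|---|---|---|
| Exclusion 25, yellow fever and live attenuated vaccines | Carboplatin | Prohibited on carboplatin in 5.2.4 |
| Exclusion 27, prophylactic phenytoin or fosphenytoin | Cisplatin or carboplatin | Prohibited in 5.2.3 and 5.2.4 |
| Inclusion 8, renal function (at least 60 mL/min for cisplatin, 30 mL/min for carboplatin) | Each, with its own threshold | GFR estimated before each platinum dose (9.7); reduced carboplatin doses in Table 5.6 |
| Exclusion 26, hemorrhagic tumors | Carboplatin | None in 5.1.7, Table 5.5, 5.1.7.4 with Table 5.6, 5.2.4 or the schedule of events |

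Hemorrhagic tumors are mentioned only in the three exclusion lists. The other three rules each have a treatment-phase counterpart, which suggests that the omission for exclusion 26 is an oversight.

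**Step 3: could a site judge the matter at the switch without a new procedure?** Platinum is limited to 6 cycles of 21 days. On schedule, Cycle 6 Day 1 falls (6 − 1) × 21 = 105 days after the first dose, and 105 / 7 = 15 weeks. Section 6.2.8 states: "Frequency of tumor assessments will be every 6 weeks to Week 24". So any on-schedule switch falls in the 6-weekly imaging period, with at least a baseline scan on file. This has a limit. Appendix 17.3.2.8 requires chest and abdomen, with other sites only where disease is suspected, and asks for no reading of hemorrhage. A scan may therefore not settle the question, and clinical information is needed too.

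**Step 4: size.** The number affected is the number of subjects multiplied by the share starting cisplatin, the share of those who switch, and the share of switchers with a hemorrhagic tumor. The documents give 105 subjects and none of the three shares, so no estimate can be derived.

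**The case against.** There is a fair case that the text already works.

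- **The wording looks forward.** At screening no subject is yet receiving carboplatin in the study, so exclusion 26 must refer to treatment to come. Read that way, it reaches later switchers, and the site has the rule in hand. This reading is open. Against it stand the opening sentence of the list, which speaks of entry, and a Table 5.5 row with no condition attached. Where a safety rule bears two readings, it is worth stating which one is meant.
- **The Investigator has discretion.** Section 5.1.7 is headed as guidelines, lists withholding and reducing beside switching, leaves dose reduction and withholding to the Investigator, and invites contact with the medical monitor. This stands. A reader might infer that the protocol forces carboplatin on a subject with a bleeding tumor; the documents do not support that.
- **Blood counts are controlled.** Section 5.1.7.4 holds repeat carboplatin until platelets have recovered, Table 5.6 cuts the dose when platelets fall below 50,000, and blood-count results must be available before dosing. Cisplatin has thrombocytopenia rules of its own. This stands too. The documents give no reason for exclusion 26 and no measure of extra bleeding risk on carboplatin compared with cisplatin, so a claim of demonstrated harm would go beyond them.
- **Prescribing information is referred to.** Section 5.1.7 and the note to Table 5.6 point to it, but for managing toxicities. Neither pointer names hemorrhagic tumors, and the content is not in the documents, so it cannot be said whether it closes the gap.

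These arguments lower the priority. They do not supply the missing condition at the switch.

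**Conclusion.** The inconsistency is real and small. The entry restriction in exclusion 26 is not repeated at the permitted switch in 5.1.7, at the instructed switch in Table 5.5, or among the carboplatin rules in 5.2.4. The conclusion rests on reading the list in 4.1.2 as an entry check. If the sponsor meant exclusion 26 to apply whenever carboplatin is started, the remaining fault is only that the switch rules do not say so.

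The frequency is probably low but cannot be worked out from the documents. A reader might infer that several subjects would be exposed, or that the trial's result is at risk. Neither inference is supported: the rates needed for the first are absent, and PFS, power and the planned analyses do not depend on this rule.

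This is a cheap improvement for patient safety, of low priority.

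**What to change.** 1. In Sections 5.1.7 and 5.2.4 add: *Carboplatin must not be started, including by switch from cisplatin, in a subject with a hemorrhagic tumor (exclusion 26), as judged and documented by the Investigator from available clinical and imaging information; in that case withhold, reduce or discontinue cisplatin as the toxicity rules allow and continue the other study drugs.*
2. In the neuropathy row of Table 5.5 add: *unless the subject has a hemorrhagic tumor, in which case discontinue cisplatin and continue patritumab/placebo and cetuximab.*

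The second item says discontinue, and not reduce, on purpose. The row as it stands takes a subject with sensory neuropathy of Grade 2 or higher off cisplatin, and the exception should not become a way of continuing it at a lower dose. Continuing the other drugs is already the policy of 5.1.7.

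The cost is one sentence in two sections, one clause in a table, and one documented judgment at each switch. No new assessment is required. The downside is that a few subjects may receive less platinum than they would after a switch. The SAP's analyses need no change.

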#### **4.1.3. Removal of Subjects From Therapy**

Any subject may withdraw from the study treatment or from the study at any time without specifying a reason. If a subject withdraws from the study treatment or study, the reason for withdrawal will be recorded on the eCRF. The Investigator will complete and report the observations as thoroughly as possible up to the date of withdrawal including the date of last treatment and the reason for withdrawal.

#### **4.1.4. Reasons for Discontinuation of Study Treatment**

Reasons for discontinuation of a subject from the study include: PD as per RECIST 1.1 or clinician's assessment, AE, death, withdrawal of consent by subject, significant protocol violation, or sponsor decision to terminate the study.

In the event of a decision to discontinue study drug treatment the investigator will contact the subject directly to explain the circumstances requiring study treatment to be stopped. The subject will be instructed to attend the safety follow-up visit required by the study protocol, and the treating physician will discuss alternative treatment options with the subject.

The reason for discontinuation will be recorded.

Subjects may be withdrawn from the study after signing informed consent for the following reasons:

- Adverse Event
- Lost to Follow-up
- Withdrawal of Consent by Subject
- Physician Decision
- Death
- Pregnancy
- Progressive Disease

- Study Terminated by Sponsor
- Other

All subjects who are withdrawn from the study should complete protocol specified withdrawal procedures, unless they withdraw their consent (Section 4.1.5).

Elevations in AST/ALT and/or total bilirubin that meet the criteria described in Table 4.1 require permanent discontinuation of the subject from patritumab/placebo and cetuximab.

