#### **4.1.1. Inclusion Criteria**

Subjects must satisfy all of the following criteria to be included in the study:

1. Adult subjects  $\geq 18$  years old
2. Histologically confirmed recurrent disease or metastatic SCCHN tumor and/or from its lymph nodal metastases originating from the oral cavity, oropharynx, hypopharynx, and larynx
3. Heregulin expression level is required
  - Samples must be taken from subjects who have recurrent or metastatic disease (rec/met). These samples can be from either rec/met archived or fresh biopsy samples (either primary tumor or metastases)
  - No cancer treatment between time of biopsy and submission of sample
  - Surgical or core needle biopsy is acceptable
  - Fine-needle aspiration or cytology is not acceptable for biopsies
4. HPV status or p16 (surrogate for HPV) is required. These results must come from tumor tissue. These results may be obtained from either a local lab or samples sent to the central lab
  - HPV or p16 status can be from any tumor biopsy material from initial diagnosis
5. Measurable disease per Response Evaluation Criteria in Solid Tumor (RECIST) Version 1.1

6. Eastern Cooperative Oncology Group (ECOG) performance status 0 or 1
7. Hematological function, as follows:
  - Absolute neutrophil count (ANC)  $\geq 1.5 \times 10^9/L$
  - Platelet count  $\geq 100 \times 10^9/L$
  - Hemoglobin  $\geq 10$  g/dL
8. Renal function, as follows:
  - Estimated serum creatinine clearance (mL/min) or GFR  $\geq 60$  mL/min for cisplatin and  $\geq 30$  mL/min for carboplatin
9. Hepatic function, as follows:
  - Aspartate aminotransferase (AST)  $\leq 2.5$  x upper limit of normal (ULN) (if liver metastases are present,  $< 5$  x ULN)
  - Alanine aminotransferase (ALT)  $\leq 2.5$  x ULN (if liver metastases are present,  $< 5$  x ULN)
  - Alkaline phosphatase  $\leq 2.0$  x ULN (if bone or liver metastases are present,  $< 5$  x ULN)
  - Bilirubin  $\leq 1.5$  x ULN
10. Prothrombin time or partial thromboplastin time  $\leq 1.5$  x ULN
11. Women of childbearing potential must have a negative serum pregnancy test performed within 14 days prior to enrollment (where demanded by local regulations, test may be required within 72 hours prior to enrollment)

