**Table 4.1: Criteria for Permanently Discontinuing Study Drug for Elevations of Aminotransferase and/or Bilirubin**

Discontinuation Criteria	Confirmation Period
Serum AST or ALT > 3 x ULN and total bilirubin of > 2 x ULN	Repeat testing 3-7 days later to confirm laboratory results
AST or ALT > 5 x ULN	Repeat testing 3-7 days later to confirm laboratory results

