### 5.1.7.1. Dose Modification of Patritumab

Patritumab is contraindicated for subjects with known hypersensitivity to either the drug substance or inactive ingredients in the drug product. In previous patritumab studies, the most common toxicities that occurred were rash, diarrhea, vomiting, nausea, fatigue, dyspnea, and skin and subcutaneous tissue disorders. Table 5.1 and Table 5.2 pertain to patritumab dose modifications.

If the initial loading dose of 18 mg/kg is not tolerated, infusion time can be extended to a maximum of 120 minutes for subjects unable to tolerate the 60 minute infusion. Patritumab/placebo is to be withheld from a subject experiencing a CTCAE Grade 3 AE, and resumed at the next regularly scheduled patritumab dosing (maintenance dose of 9 mg/kg) only after resolution of the AE to Grade 0 or 1 (or baseline grade if higher than Grade 1).

If a rash or mucositis occurs following the initial dose of patritumab 18 mg/kg, then hold the patritumab until the AE resolves to Grade 0 or 1 (or baseline grade if higher than Grade 1). If the rash or mucositis has not resolved, then hold cetuximab 250 mg/m^2 until the AE resolves to Grade 0 or 1 (or baseline grade if higher than Grade 1). If a rash or mucositis occurs on the maintenance dose of patritumab at 9 mg/kg, hold patritumab until the AE resolves to Grade 0 or 1 (or baseline grade if higher than Grade 1) and then decrease patritumab dosing to 6 mg/kg. If the AE does not resolve, hold the next dose of cetuximab until resolution to Grade 0 or 1 (or baseline grade if higher than Grade 1).

Left ventricular ejection fraction will be monitored throughout the study (see Section 9.11.1) for possible effects of patritumab treatment on cardiac function. Dose modification or suspension of patritumab treatment will be based on decreased LVEF, as outlined in Table 5.1.

For cases of ILD, refer to Section 9.3.2.

Both patritumab/placebo are to be withheld from a subject experiencing a Grade 4 AE.

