**Table 5.1: Patritumab Maintenance Dose Modification for Toxicities**

Toxicity	Withhold Criteria	Resumption Criteria	Dose Reduction Criteria	Discontinuation Criteria
All AEs a	Grade 3 or higher	Grade 0 or 1 (or baseline grade if higher than Grade 1) b	Reduce patritumab maintenance dose from 9 mg/kg to 6 mg/kg (for mucositis follow dose modification as defined above)	Failure to recover within 3 weeks

Toxicity	Withhold Criteria	Resumption Criteria	Dose Reduction Criteria	Discontinuation Criteria
Ejection fraction	Grade greater than or equal to 3, (LVEF of less than 40% or LVEF decrease of more than 20% from the baseline)	LVEF of at least 50% (or baseline) based on a repeat echocardiogram or MUGA scan performed in 3 weeks	Reduce patritumab maintenance dose from 9 mg/kg to 6 mg/kg	LVEF that does not recover within 3 weeks: Decreased $\geq$ Grade 3 <40% >20% decrease from baseline

a For elevations of aminotransferase (AST/ALT) and/or bilirubin, please see Section 4.1.4.

b Patritumab/placebo dosing may be resumed upon consultation with the Sponsor's medical monitor if the event has resolved to Grade 2.

MUGA = multigated acquisition (scan); LVEF = left ventricular ejection fraction.

Dose delays/reductions for toxicities related to patritumab are summarized in Table 5.2.

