**Table 5.2: Dose Delays/Reductions for Toxicities Related to Patritumab**

Grade	Action
1	Continue current dose level
2	Continue current dose level
3	Discontinue patritumab/placebo for up to 3 weeks until the event has recovered to Grade 1 or baseline. a Administer patritumab at a dose that is decreased by one dose level for subsequent cycles. A maximum of 1 dose reduction from the 9 mg/kg IV maintenance dose to 6 mg/kg IV maintenance dose will be permitted. No dose reductions below patritumab 6 mg/kg will be allowed.
4	Discontinue patritumab/placebo for up to 3 weeks until the event recovers to Grade 1 or baseline. a Discuss the event with the sponsor's Medical Monitor or designee before restarting patritumab/placebo. If the investigator and the sponsor's Medical Monitor/designee agree, the weekly maintenance dose will also be decreased from 9 mg/kg IV to 6 mg/kg IV.

a If the subject fails to recover to Grade 1 or baseline and dose must be delayed >3 weeks, the subject will be withdrawn from all study treatment, but should continue to undergo all follow-up evaluations

To receive patritumab, a subject's ANC must be  $\geq 1.5 \times 10^9/L$  ( $\geq 1500/mm^3$ ) and platelet count must be  $\geq 100 \times 10^9/L$  ( $\geq 100,000/mm^3$ ). Patritumab may be withheld for up to 3 weeks to allow cell counts to recover to these values. Dose administration may be delayed no more than 3 weeks to allow for recovery. If the dose is delayed more than 3 weeks, the subject will be withdrawn from study treatment, unless discussed and agreed with the sponsor.

All subjects should be carefully monitored for possible infusion reactions during the administration of patritumab/placebo. If, during infusion, a subject experiences mild to moderate symptoms suggestive of infusion reaction (such as fever and chills, with or without nausea/vomiting, pain, headache, dizziness, dyspnea, hypotension), slow down the infusion up to 120 minutes (see Section 3.1.2.1 for administration of patritumab/placebo). All subsequent infusions should be administered at the same slow rate (up to 120 minutes).

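### Protocol Section 4.1.4 stops patritumab/placebo permanently for confirmed hepatic elevations, while Table 5.2 and the Section 5.1.7.1 text let it resume; which rule covers an isolated bilirubin rise is unclear

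*Protocol*

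**What the plan says.** Section 4.1.4 of the protocol sets the hepatic stopping rule: "Elevations in AST/ALT and/or total bilirubin that meet the criteria described in Table 4.1 require permanent discontinuation of the subject from patritumab/placebo and cetuximab". The criteria stand in Table 4.1, which is titled "Criteria for Permanently Discontinuing Study Drug for Elevations of Aminotransferase and/or Bilirubin" and has two rows: "Serum AST or ALT > 3 x ULN and total bilirubin of > 2 x ULN" and "AST or ALT > 5 x ULN". Both call for a confirmatory repeat 3-7 days later.

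Section 5.1.7.1 covers patritumab dose modification in three places:

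- **Text.** For Grade 3: "Patritumab/placebo is to be withheld from a subject experiencing a CTCAE Grade 3 AE, and resumed at the next regularly scheduled patritumab dosing", once the event has recovered. For Grade 4 it says only that dosing is withheld.
- **Table 5.1, row for all adverse events.** Withhold at Grade 3 or higher, with criteria for resuming, reducing and discontinuing. Its footnote a reads: "For elevations of aminotransferase (AST/ALT) and/or bilirubin, please see Section 4.1.4".
- **Table 5.2, toxicities related to patritumab.** Grades 1 and 2 continue. Grade 3 is held for up to 3 weeks, and then: "Administer patritumab at a dose that is decreased by one dose level for subsequent cycles". Grade 4 is held for up to 3 weeks, and restart is possible if the investigator and the sponsor's medical monitor agree. Its own footnote withdraws the subject from treatment only if recovery takes longer than 3 weeks.

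**The concern.** A confirmed aminotransferase elevation attributed to patritumab falls under both sets of rules. One ends patritumab/placebo for good; the other holds it and provides for restart. Two sites could handle the same event differently, and each could point to protocol text. Section 5.1.7 raises the stakes, because a subject who must discontinue patritumab/placebo is withdrawn from the study. The choice of table therefore affects exposure to the experimental drug as well as compliance with a safety stop.

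The second problem is the route for bilirubin. Section 4.1.4, the title of Table 4.1 and footnote a of Table 5.1 all announce elevations of aminotransferase and/or bilirubin. A site that follows the footnote with a raised bilirubin and unremarkable aminotransferases arrives at a table with no row for that case.

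**Working it through.** There is no power, event-count or alpha figure to reproduce. The check is a comparison of passages plus a logical test of Table 4.1.

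**Step 1. One event, four instructions.** Take a confirmed AST or ALT above 5 x ULN, attributed to patritumab.

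| Place | Instruction for patritumab/placebo | Defers to Section 4.1.4? |
|---|---|---|
| Section 4.1.4, Table 4.1 | Permanent stop | It is the rule |
| Section 5.1.7.1 text | Grade 3: withhold, then resume. Grade 4: withhold | No |
| Table 5.1, all adverse events | Grade 3 or higher: withhold, then resume on recovery | Yes, footnote a |
| Table 5.2 | Grades 1-2: continue. Grade 3: hold, then restart lower. Grade 4: hold, restart by agreement | No |

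The documents do not print the CTCAE cut-offs for AST and ALT, so the grade of this event cannot be read from them. For Table 5.2 the grade does not matter: 0 of its 4 grade rows give an immediate permanent stop. The same holds for an event meeting the combined criterion. Of the three places in Section 5.1.7.1, one carries the deferral and two do not.

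**Step 2. Can bilirubin alone meet Table 4.1?** Write A for the higher of AST and ALT, and B for total bilirubin, both in multiples of ULN. Table 4.1 is met when

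(A > 3 and B > 2) or A > 5.

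If A is at most 3, both parts are false whatever B is. Numerically, with A = 1 and B = 2.1, 3.1, 5, 10 or 20, and with A = 3 and B = 2.1, 10 or 20, the rule is never met. So 0 of the 2 rows apply to an isolated bilirubin elevation.

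**Step 3. What then governs that elevation?** Footnote a points to Section 4.1.4, which has no criterion for it. It does not say whether the Table 5.1 row still applies. The Section 5.1.7.1 text withholds for any Grade 3 or Grade 4 adverse event, and Section 9.7 requires laboratory values of Grade 3 or higher to be recorded as adverse events. Table 5.2 applies if the event is attributed to patritumab. Rules therefore exist that could cover the case, but no passage says which of them does.

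**The case against.** The best defence is that a specific rule prevails over a general one. Section 4.1.4 is specific, speaks of permanent discontinuation, and is cross-referenced from Table 5.1, which sits beside Table 5.2 in the same section. Other permanent stops also lie outside the grade table: interstitial lung disease in Section 9.3.2 and severe infusion reactions in Section 5.1.7.1. On bilirubin, the wording of Section 4.1.4 is limited to elevations that satisfy Table 4.1, so the loose phrase adds no criterion of its own.

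Much of this stands as evidence of intent, and footnote a is a strong signal. It does not remove the conflict. The footnote belongs to one row of Table 5.1; Table 5.2 is a separate table with its own footnote and no such pointer. The Section 5.1.7.1 text does refer the reader elsewhere for interstitial lung disease, but not for hepatic events. On a safety stop, a site should not have to infer which passage wins. The limiting words in Section 4.1.4 settle what that section requires, but not what footnote a means by sending bilirubin elevations there.

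Three stronger readings are tempting, and the documents do not support them.

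- **That the stopping rule collides with the entry limit for liver metastases.** Inclusion criterion 9 admits such subjects with AST and ALT below 5 x ULN and bilirubin at most 1.5 x ULN. The stop needs a value above 5 x ULN, or bilirubin above 2 x ULN alongside the aminotransferase rise. These ranges do not overlap: 0 of 75,500 eligible grid points meet Table 4.1 at entry, and a repeat test is required as well. Whether the rule should take account of baseline is a clinical preference, not an inconsistency.
- **That two of the three study drugs are stopped or resumed depending on the table.** The resumption passages cited here concern patritumab/placebo only.
- **That an isolated bilirubin elevation has no withhold rule, leaving a patient-safety gap.** The Section 5.1.7.1 text still withholds at Grades 3 and 4.

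**Conclusion.** The protocol contradicts itself on whether patritumab/placebo may resume after an event that meets Table 4.1. For Table 5.2 this holds at every grade, given attribution to patritumab. For the Section 5.1.7.1 text it holds at Grade 3, the only grade for which that text provides resumption. The smaller point also holds: footnote a of Table 5.1 sends bilirubin elevations to a section with no bilirubin-alone criterion, so the governing rule for that case is unclear.

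The conclusion rests on the wording alone and needs no assumption about CTCAE cut-offs. How many subjects would be affected cannot be estimated, because the documents give no expected frequency of such elevations. This should be corrected, because it is an opposite instruction on a safety stop and not merely a missing detail. It does not alter the planned sample size or analysis.

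**What to change.** Reconcile Section 4.1.4 and Table 4.1 with Section 5.1.7.1 and Tables 5.1 and 5.2:

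1. State in Table 5.2 and in the Section 5.1.7.1 text which rule prevails for AST, ALT and bilirubin events.
2. Align the bilirubin wording of Section 4.1.4, the title of Table 4.1 and footnote a of Table 5.1 with the criteria that Table 4.1 contains.
3. Say which passage governs an isolated bilirubin elevation.

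The clinical team decides the rule; no threshold or action is proposed here. The cost is protocol amendment wording and its usual approval. No extra tests are needed, since AST, ALT and total bilirubin are already in the serum chemistry panel of Section 9.7.
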